Study Protocol and Statistical Analysis Plan

Title of Study: Effects of Transcutaneous Vagus Nerve Stimulation (taVNS) in Individuals with Primary Dysmenorrhea: A Randomized Controlled Study

NCT Number: NCT06146569

Date of Document: September 18, 2023

Table of contents

	Page number
Study Protocol	3
Objectives	3
Design	3
Methods	3
Statistical Analysis Plan	4

Study Protocol

Objectives:

This study aims to investigate the effects of transcutaneous auricular vagus nerve stimulation (taVNS) on pain, functional and emotional symptoms, and physical performance in individuals with primary dysmenorrhea (PD).

Design:

A small randomized controlled trial design was conducted online at two time points: 1) baseline/pre-test and 2) post-test (one week after pre-test). Data were collected by face-to-face interview method.

Participants will be randomly assigned to one of two conditions: 1) intervention (women received taVNS treatment) or 2) sham (Sham applications were applied using a current-free headset specifically designed for this purpose. Participants observed the device's functionality but supplied no current).

The study was approved by the Artvin Çoruh University Rectorate Scientific Publications Ethics Committee (date: 18/09/2023, procedure number: E-105136) and was by the ethical standards of the World Medical Association (Declaration of Helsinki).

Methods:

Sample and Recruitment. Women who had never given birth before participated in the study. To participate in the research, the following criteria must be met: 1) being diagnosed with PD according to the No. 345 Primary Dysmenorrhea Consensus Guidelines; 2) an NRS score of at least three during menstruation before treatment; 3) being a woman between the ages of 18-40; 4) a regular menstrual cycle of 28 ± 7 days; 5) being nulliparous; 6) no history of brain surgery, tumor, or intracranial metal implantation; 7) No chronic genitourinary infection or alcohol or drug use. Potential participants were invited to study at Artvin Çoruh University through voice announcements and brochures. Following diagnosis with primary dysmenorrhea at Artvin State Hospital, those who met the study's inclusion criteria received treatment at Artvin Çoruh University Physiotherapy Laboratory between November 2023 and January 2024.

Procedure. The current of taVNS was applied bilaterally from the tragus and turbinate parts of the ear with the VagustimTM device. The current frequency used in modulation mode is 10 Hz, and the pulse width was 300 μ s (In modulation mode, the pulse rate and width are automatically changed in a loop pattern. The pulse width was reduced by 50% from its original setting in 0.5 seconds; then, the pulse rate was changed in 0.5 seconds, reduced by 50% from the original setting. Total cycle time is 1 second.). The current intensity was applied for 5 minutes, keeping the current constant where the participant felt comfortable. Sham applications were applied using a current-free headset specifically designed for this purpose. Participants observed the device's functionality but supplied no current.

Measures.

Numerical Rating Scale (NRS). Data was queried separately for lower abdominal, waist, and bilateral thigh pain. Participants were required to complete an NRS questionnaire through the Google Forms web survey platform (Google LLC, Mountain View, CA, USA) before bed at

night on days 1, 2, and 3 of two consecutive menstrual cycles. The questionnaire was based on the most severe pain they experienced during the day. The minimum score of the NRS is 0, and the maximum score is 10. Higher scores are associated with more severe pain intensity.

Pressure Pain Threshold (PPT). Fabrication Enterprises, Inc., used a Push-Pull Force Gauge® (1200-304) to measure the pressure pain threshold. This handheld algometer allows linear force application ranging between 0 and 10 kg (22 lb × ¼ lb and 10 kg × 100 g). Initially, two exercises were performed on the dominant forearm's extensor muscles to familiarize patients with the equipment. The evaluator positioned the algometer perpendicular to each point and applied gradual pressure at a constant rate of approximately 0.5 kg/cm²/s. The pressure was increased until the participant reported feeling pain. Each point was evaluated three times, and the average value was recorded. The measurement was performed on five reference points in the abdomen and one reference point in the lumbar spine, as in a previous study where pain was evaluated in PD.

Menstrual Symptom Questionnaire (MSQ). The scale consists of 22 items and uses a 5-point Likert-type format. Participants were asked to rate the severity of their menstrual symptoms on a scale of 1 (never) to 5 (always). The scale contains three subscales: 'Negative Effects/Somatic Complaints' (items 1-13), 'Menstrual Pain Symptoms' (items 14-19), and 'Coping Methods' (items 20-22). The maximum score on the scale is 110, and the minimum score is 22. MSQ score is calculated by taking the average score of all items in the scale. High scores are associated with increased menstrual symptoms.

Functional and Emotional Measure of Dysmenorrhea (FEMD). Scale consisting of 14 items, evaluates dysmenorrhea functionally and emotionally with a 5-point Likert-type item. The reliability and validity study of the scale developed in 2012. As the scores obtained from the scale with a minimum score of 14 and a maximum score of 70 increase, the functional and emotional impact of dysmenorrhea also increases.

Hamilton Anxiety Scale (HAM-A). Patients with chronic pain often experience mood disorders, such as depression and anxiety. The Hamilton Anxiety Scale (HAM-A) was used to assess the intensity of anxiety symptoms. The scale measures both mental and physical anxiety with 14 symptom-defined items. Each item is scored from 0 (not present) to 4 (severe). The total score range is 0-56. On the anxiety scale, scores of 17 or below indicate mild anxiety, while scores of 18-24 indicate moderate anxiety, and scores of 25-30 indicate severe anxiety.

6-Minute Walk Test (6MWT). The 6-Minute Walk Test (6MWT) was evaluated submaximal functional capacity. 6MWT measures the maximum distance participants can walk as quickly as possible for six minutes.

Positive and Negative Affect Schedule (PANAS). For taVNS administration, the positive and negative affect was assessed before and after treatment using the Positive and Negative Affect Schedule (PANAS). This 5-point Likert-type scale was developed in 1988 and includes 20 items: 10 positive and ten negative. A score range of 10-50 assesses both positive and negative effects.

Statistical Analysis Plan

IBM SPSS version 28.0 software (IBM Corp., Armonk, NY, USA) was utilised for statistical analysis. Before the statistical analysis, the Shapiro-Wilk normality test was used to assess data distribution because of $n < 50$. Demographic data and clinical baseline variables were compared among the 2 groups by independent samples t-test for continuous variables and a χ^2 test for categorical variables. Continuous variables were expressed as mean \pm standard deviation (SD), while categorical variables were reported as number and frequency. The independent and paired samples t-test was compared to normally distributed variables between two groups. Two-way analysis of variance (ANOVA) was used for multiple comparisons of normally distributed

variables. The effects of stimulation on pain, pressure pain threshold, menstrual symptoms, and physical performance were calculated using a mixed ANOVA, where the dependent variables were pain, pressure pain threshold, menstrual symptom, and physical performance score, and the independent fixed variables were time, stimulation group (taVNS and sham), and interaction term was group vs time. Post hoc comparisons were carried out when appropriate using Bonferroni correction for multiple comparisons. Greenhouse-Geisser correction was applied when the assumption of sphericity was violated. In the F tests, partial eta squared (η^2) was used as an effect size indicator, elucidated as small, 0.01; medium, 0.06; and large, 0.14. In the t-tests, Cohen's d (d) was used as an effect size indicator, elucidated as small, 0.2; medium, 0.5; large, 0.8. A p value of <0.05 was considered statistically significant.

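### No measure or SAP analysis records adverse effects or tolerability in either arm, so taVNS and sham cannot be compared on unwanted effects

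*Combined protocol and SAP*

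**What the plan says.** The objective is limited to possible benefits: "This study aims to investigate the effects of transcutaneous auricular vagus nerve stimulation (taVNS) on pain, functional and emotional symptoms, and physical performance".

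Under Procedure, comfort governs exposure in the active arm: "The current intensity was applied for 5 minutes, keeping the current constant where the participant felt comfortable". The other arm receives no current: "Sham applications were applied using a current-free headset specifically designed for this purpose". The section gives no instruction to note the level reached, discomfort, or a session that was cut short.

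Under Measures there are seven instruments: NRS, PPT, MSQ, FEMD, HAM-A, 6MWT and PANAS. The NRS is a bedtime web form, completed at "night on days 1, 2, and 3 of two consecutive menstrual cycles", and its content is pain by body site: "Data was queried separately for lower abdominal, waist, and bilateral thigh pain".

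The SAP's mixed ANOVA names pain, pressure pain threshold, menstrual symptoms and physical performance as its dependent variables. The SAP has no summary of harms or tolerability. The table of contents lists Objectives, Design, Methods and the SAP, so nothing suggests that a safety section existed and was removed.

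**The concern.** The intervention is an electrical current applied to both ears, at a level each participant finds comfortable. How well it was tolerated, and at what level, is a basic fact about the treatment. If the plan is followed to the letter, every form can be completed without anyone noting a local ear complaint, a low intensity ceiling or an abandoned session.

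Information of this kind is hard to recover afterwards if nobody asks at the time. The trial also has a good comparator for device-related complaints in its current-free arm, and the plan does not use it for that purpose. A reader who later finds no harms in the report could mistake missing data for evidence of safety.

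**Working it through.** **Does any planned record capture an unwanted effect of the session?** The plan gives no figure to reproduce, so the first check sets the instruments side by side.

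- NRS: abdominal, waist and thigh pain. No other complaint is asked about.
- PPT: pressure threshold at abdominal and lumbar points.
- MSQ: menstrual symptoms. The subscale with negative effects in its name rates menstruation, not stimulation.
- FEMD: functional and emotional impact of dysmenorrhea.
- HAM-A: anxiety symptoms, mental and physical.
- 6MWT: walking distance.
- PANAS: positive and negative affect before and after treatment. Where the text speaks of negative effects, it means affect.
- SAP: no count of events, complaints, early stops or intensity.

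No record is found in either arm.

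**What could a trial of this size say if it did record?** This part is illustrative.

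Inputs: the SAP gives only n below 50, as the reason for using the Shapiro-Wilk test. No planned total or allocation ratio is stated. I read n as the total, assume roughly equal arms, and take 10 to 25 per arm. About 24 per arm is close to the most that this reading allows.

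Formulas, for n participants in one arm and a true rate p:

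- Chance of at least one case: 1 − (1 − p)^n
- One-sided 95% upper bound with zero events: 1 − 0.05^(1/n)
- Two-sided exact 95% upper limit with zero events: 1 − 0.025^(1/n)

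| n per arm | At least one case, p = 5% | At least one case, p = 10% | Zero events, one-sided bound | Zero events, two-sided limit |
|---|---|---|---|---|
| 10 | 40% | 65% | 25.9% | 30.8% |
| 15 | 54% | 79% | 18.1% | 21.8% |
| 20 | 64% | 88% | 13.9% | 16.8% |
| 24 | 71% | 92% | 11.7% | 14.2% |
| 25 | 72% | 93% | 11.3% | 13.7% |

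For n = 24: 1 − 0.95^24 = 0.708; 1 − 0.90^24 = 0.920; 1 − 0.05^(1/24) = 0.117; 1 − 0.025^(1/24) = 0.142.

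A trial this small can detect or bound only fairly common effects. At a true rate of 1% the chance of seeing any case is 10% (n = 10) to 22% (n = 25). Without a record, none of these statements can be made.

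**The case against.** The best defence is that the instruments are not blind to harm. If stimulation increased pain, lowered the pressure threshold, or worsened menstrual symptoms, anxiety or mood, the NRS, PPT, MSQ, HAM-A or PANAS could show it by arm. The protocol also places PANAS before and after treatment and links it to taVNS administration, so it cannot be dismissed as unrelated to the sessions, although the text does not say whether it is given at each one. This stands, and it rules out the reading that the trial could say nothing at all about harm. It does not supply an event record: a sore ear or a session abandoned for discomfort would not be identifiable from any of these scores.

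A reader might infer from the criterion "no history of brain surgery, tumor, or intracranial metal implantation", together with the comfort setting, that the plan itself regards the current as hazardous. The documents give no reason for either, so the point should not rest on that inference.

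A reader might also infer that web follow-up runs well past the last visit, and try to calculate how much of the at-risk time a one-week query would cover. The documents do not say where the pre-test falls in the cycles, when stimulation starts or how many sessions there are. The first diary cycle may be a pre-treatment baseline. The Design section describes the trial as online and the data collection as face-to-face. No coverage figure can be supported.

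Finally, asking about unwanted effects has a cost when the sham delivers no current and pain is self-rated, because the question may prompt participants to guess their arm. Placing it after the efficacy ratings of the same day does not protect ratings made later. This stands, and it limits when the question should be asked.

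**Conclusion.** The omission is real and can be checked directly: neither arm has any planned record of adverse effects, intensity reached or early stops, and the SAP has no analysis of them. The consequence is specific. Any efficacy conclusion stands or falls on other grounds, but the trial could not compare the arms on unwanted effects or weigh a pain benefit against them.

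The omission itself needs no assumption about numbers. The figures for its size depend on the assumed 10 to 25 per arm, on about equal allocation, and on every case being noted when it occurs. The change is one that should be made; it does not put the main comparison in doubt. Nothing in the documents suggests that harms occurred or were withheld.

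**What to change.** In both arms:

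1. For each session, log the intensity setting reached (none for sham), any early stop, and any complaint the participant volunteers. Do not prompt at this point.
2. At the one-week post-test, after all efficacy ratings, ask one open, neutrally worded question on unwanted effects (what, how severe, start and stop), in identical words in both arms.
3. Ask it again on the existing web form, but only after the last NRS rating of the final diary cycle.
4. In the SAP, report the number and percentage of participants with any unwanted effect, by arm, with exact two-sided 95% confidence intervals and no significance test.

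The cost is a short session log, some staff time to review the answers, and one table; no extra visit is needed. A residual risk remains: if diary ratings follow the post-test, the question asked there may lead some participants to guess their arm before giving them.

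The document is dated September 2023 and gives treatment as starting in November 2023, so the change could have been made before the first session. If data collection is already complete, the report should state that unwanted effects were not systematically collected, so that their absence is not read as evidence of safety.

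### The plan does not say that outcome assessors are masked or separate from the person delivering stimulation, so every outcome except the self-completed NRS is open to influence from an assessor who knows the arm

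*Combined protocol and SAP*

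**What the plan says.** **Mode of collection.** The Design section gives one general statement: "Data were collected by face-to-face interview method". The sentence just before it reads "A small randomized controlled trial design was conducted online at two time points". Under Measures, the NRS follows a third route: "Participants were required to complete an NRS questionnaire through the Google Forms web survey platform", filled in at night on days 1 to 3 of two cycles. The entries for MSQ, FEMD, HAM-A and PANAS do not say who administers the scale or how.

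**Hand-applied and effort-dependent measures.** For PPT, "The evaluator positioned the algometer perpendicular to each point and applied gradual pressure at a constant rate of approximately 0.5 kg/cm²/s", and "The pressure was increased until the participant reported feeling pain". The 6-minute walk test (6MWT) records distance at the participant's fastest pace. HAM-A items are scored 0 to 4. Only PPT names an evaluator, and nothing is said about what that person knows.

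**Stimulation.** Under Procedure, for the active arm: "The current intensity was applied for 5 minutes, keeping the current constant where the participant felt comfortable". Sham is given through a different headset, built to carry no current. That sham is the only feature in the document related to masking, and it is directed at participants.

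**Analysis.** The SAP tests pain, PPT, menstrual symptoms and physical performance in a mixed ANOVA with a group-by-time term. It also provides for t-tests between groups.

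**The concern.** A sham protects the comparison only on the participant's side. If the person who asks the questions, presses the algometer or runs the walk test knows the arm, expectation can enter through prompting, through interpretation of answers, through the pressure ramp or through encouragement. This would happen even with a sham that no participant could detect, so it is a separate problem from participants guessing their arm.

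At stake are PPT, MSQ, FEMD, HAM-A, PANAS and 6MWT, which is every listed outcome apart from the NRS. A shift at post-test that differs by arm has the same form as the group-by-time effect the SAP looks for. No later adjustment can remove it, because nothing recorded would identify it.

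**Working it through.** The plan states no figure on this point, so there is none to reproduce. The check has two parts.

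**1. What the text supports, step by step**

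| Step | Basis | Status |
|---|---|---|
| No masking or separation of assessors is provided for | Design, Procedure, Measures and SAP are all silent | Verifiable |
| The operator knows the arm | Different sham headset; active current set to comfort; no coded device or third-party set-up described | Very likely, but inferred |
| The operator also assesses outcomes | Not stated either way; nothing prevents it | Open |
| Scales other than the NRS are given by interview | General Design sentence only, in tension with the online statement | Stated, but needs reconciling |
| The NRS is exposed by this route | Self-entered on a web form at night | No |

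On PPT the plan adds "Each point was evaluated three times, and the average value was recorded". Averaging three readings reduces random error. A systematic difference in how the ramp is applied in one arm would be present in all three readings and would survive the averaging.

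**2. Illustration of size**

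Inputs:
- Significance level 0.05, from the SAP. Two-sided testing is assumed.
- Arm sizes of 12, 20 and 24, assumed. The SAP says only that n is below 50; 24 per arm gives 48.
- Assessment shift d of 0.2 or 0.3 SD of the analysed score, assumed.
- True treatment effect zero.
- Unpaired t-test, assumed. With one score per participant at each of two time points, the group-by-time F test is the square of the unpaired t-test on change scores. For that test, the SD is the SD of change.

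Formula: P(significant, favouring taVNS) = P(T > t₀.₉₇₅), where T is noncentral t with df = 2n − 2 and noncentrality d·√(n/2).

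| n per arm | df | Critical t | d = 0 | d = 0.2 (noncentrality) | d = 0.3 (noncentrality) |
|---|---|---|---|---|---|
| 12 | 22 | 2.074 | 2.5% | 6.8% (0.490) | 10.4% (0.735) |
| 20 | 38 | 2.024 | 2.5% | 9.0% (0.632) | 15.0% (0.949) |
| 24 | 46 | 2.013 | 2.5% | 10.0% (0.693) | 17.3% (1.039) |

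For n = 12 and d = 0.2, the noncentrality is 0.2 × √6 = 0.490. A normal approximation gives close values at 24 per arm: 10.3% for 0.2 SD and 17.9% for 0.3 SD. The error rate rises with arm size because a fixed bias is detected more readily as precision improves.

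**The case against.** The strongest reply is that silence is not evidence of an unmasked assessor. The document does not say who fits the headset or sets the current, and the PPT evaluator may have been a different person who did not know the arm. This stands in part. A reader might infer that assessors were unmasked, or that operator and assessor were the same person; the text supports neither as fact. It does support the narrower statement that the plan contains no safeguard.

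Second, the interview sentence cannot cover all data, since the NRS was self-entered and the trial is also described as online. For MSQ, FEMD and PANAS, interviewing is therefore the only collection mode the plan states, but not a settled one. This also stands, and it is why reconciling the statements comes first in the fix.

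Third, a reader might infer that the bias can only run towards taVNS. That is the most plausible direction, but nothing links ramp speed, prompting or encouragement to arm, and an aware assessor could overcorrect.

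Fourth, the arm sizes and shifts are assumed. That is correct: the table shows how sensitive the error rate is to a shift and does not estimate what happened.

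Finally, the NRS pain score lies outside this route. Any risk to it comes from participants recognising a sham without current, which is a separate question.

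**Conclusion.** The concern holds as a gap in the plan. Followed as written, the plan allows an assessor who knows the arm to influence every outcome except the NRS, and the group-by-time test cannot separate that influence from a treatment effect. The documents do not show that this occurred, how large it was or which way it ran.

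For scale only, a 0.2 SD shift towards taVNS with no true effect would raise the chance of a significant result in its favour from 2.5% to about 7% with 12 per arm, or 10% with 24 per arm. This rests on the assumed arm sizes, shift and unpaired t-test. The absence of any masking provision needs no assumption. That the operator knows the arm is a strong inference from the equipment described.

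**What to change.** 1. Reconcile the online, face-to-face and web-form statements, giving the mode of administration for each outcome.
2. Collect MSQ, FEMD and PANAS by self-completion on the Google Forms platform already used for the NRS, without the session operator present. The cost is small because the platform is in place. The downside is some missed items, which required fields would limit.
3. For HAM-A, PPT and 6MWT, where existing staff allow, use an assessor who did not run that participant's session and who is not told the arm. It is the assessor who must be masked; separating the roles is not enough if the assessor still learns the allocation. The document does not describe staffing, so the cost is unknown beyond some extra rostering.
4. Where step 3 is not possible, or data collection is already finished, state who assessed each measure and what they knew. Report measures without a masked assessor as assessed unmasked, and interpret them with that limitation. This costs only a few sentences.

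### The planned between-arm tests carry no baseline covariate; in a trial this small, an ANCOVA on each outcome's own baseline would remove the conditional bias from chance imbalance and lower variance without new data

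*Combined protocol and SAP*

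**What the plan says.** The Design section describes the trial with the words "A small randomized controlled trial design was conducted online at two time points", a pre-test and a post-test one week later. Its only statement on allocation is "Participants will be randomly assigned to one of two conditions". The combined document gives no ratio, sequence method, blocks, strata, concealment or holder of the list.

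No target sample size is given. The only figure is in the SAP, where the Shapiro-Wilk test is "used to assess data distribution because of $n < 50". That n is not said to be the total or the number per arm.

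Among the entry criteria (Sample and Recruitment) is "an NRS score of at least three during menstruation before treatment". On a 0 to 10 scale, baseline pain may therefore run from 3 to 10.

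On baseline differences the SAP says "Demographic data and clinical baseline variables were compared among the 2 groups by independent samples t-test for continuous variables", with a chi-square test for categorical variables. Arms are then compared by t-tests and by a mixed ANOVA in which "the independent fixed variables were time, stimulation group (taVNS and sham), and interaction term was group vs time". No baseline covariate or stratification factor appears anywhere in the SAP.

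**The concern.** With few women and a wide permitted range of pain, one arm can easily start with more pain than the other. The SAP would test for such a difference but has no step that adjusts for it.

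The two planned comparisons respond to an imbalance in opposite directions. A post-test t-test leaves part of the baseline difference in the result. The group-by-time term subtracts all of it, which is too much when pre and post are imperfectly correlated. The SAP does not say which of the two carries the conclusion, so an imbalance could make them disagree with no rule for choosing between them. Precision is also at stake: neither test makes the best use of the pre-test values.

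**Working it through.** The plan states no sample size, power or arm sizes, so there is no figure of its own to reproduce.

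**Inputs**
- From the documents: two arms, pre-test and post-test, a small trial, n < 50, no covariate in the model.
- Assumed: simple 1:1 allocation; N = 24, 40 or 48 in total, taken as equal arms of n = 12, 20 or 24; the same SD at both times; pre-post correlation r from 0.5 to 0.7.
- The between-arm t-test is read as a comparison at post-test. With two time points, the group-by-time test is a test of the difference in mean change.

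**1. How often baseline pain is unbalanced.** The baseline difference in SD units has standard error √(2/n).

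| N | n per arm | SE | 0.5/SE | P(difference ≥ 0.5 SD, either direction) |
|---|---|---|---|---|
| 24 | 12 | 0.408 | 1.22 | 22.1% |
| 40 | 20 | 0.316 | 1.58 | 11.4% |
| 48 | 24 | 0.289 | 1.73 | 8.3% |

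The last column is also the two-sided normal p-value for an observed difference of exactly 0.5 SD: 0.22, 0.11 and 0.08. A baseline test at 0.05 would therefore not flag that imbalance at any of these sizes.

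**2. What a 0.5 SD difference does to each comparison.**
- Post-test t-test, bias = r × 0.5: 0.25 SD at r = 0.5; 0.35 SD at r = 0.7.
- Group-by-time (change), bias = −(1 − r) × 0.5: −0.25 SD at r = 0.5; −0.15 SD at r = 0.7.
- The two estimates differ by the whole baseline difference: 0.25 + 0.25 = 0.35 + 0.15 = 0.5 SD.
- ANCOVA on the baseline value: bias 0 if the relation is linear with a common slope.

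On the SAP's own scale for Cohen's d, 0.2 is small and 0.5 medium.

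**3. Variance**, per unit of 2σ²/n:
- post-test: 1
- change: 2(1 − r)
- ANCOVA: 1 − r²

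ANCOVA against change is (1 − r²)/[2(1 − r)] = (1 + r)/2, which is 0.75 at r = 0.5 and 0.85 at r = 0.7: a reduction of 25% and 15%. Against the post-test t-test the reduction is r²: 25% and 49%.

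Estimating the slope costs a factor of about 1 + 1/(N − 4) for a normal covariate: 1.05 at N = 24 and 1.023 at N = 48. Against change, the ratios become 0.79 to 0.89 at N = 24 (0.75 × 1.05 and 0.85 × 1.05) and 0.77 to 0.87 at N = 48. That leaves a reduction of 11 to 21% and 13 to 23% respectively.

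**The case against.** **The mixed ANOVA already deals with baseline.** This is partly right. The group-by-time term subtracts the baseline difference, so it cannot be said to ignore an imbalance. It over-corrects, by regression to the mean, and the remaining bias is smaller than that of the post-test t-test whenever r exceeds 0.5.

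**Randomisation already allows for chance imbalance.** This stands. Averaged over allocations, both planned tests are unbiased and keep their type I error. The bias is conditional on the imbalance that occurs. The gain in variance, however, applies whether or not an imbalance occurs.

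**The sizes rest on assumptions.** This also stands. Simple 1:1 allocation, the three totals and r are not in the documents, and n < 50 appears only as the reason for a normality test. If allocation was in fact stratified by pain, step 1 would overstate the risk.

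**Stronger readings that the documents do not support.**
- A reader might infer that allocation was not concealed. The document is silent on the method; silence does not show absence.
- A reader might infer that missing blocks or strata make the next arm foreseeable. The reverse holds: with a known fixed block of 4 the next arm is guessed correctly 71% of the time, against 50% under simple randomisation. Only missing concealment gives foresight.
- A reader might take the separate sham headset as evidence on concealment. It can reveal the arm once assigned, which is a matter of blinding.
- A reader might infer that unequal arms are a serious cost. For an illustrative 0.8 SD effect at N = 48, power is 79.1% at 50:50, 77.5% at 60:40 and 74.3% at 2:1, a loss of 1.6 to 4.8 points.

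**Conclusion.** The point holds as an improvement to the analysis. It does not show that the trial is invalid. Under simple 1:1 allocation with 24 to 48 women, the chance of a baseline pain difference of 0.5 SD or more is about 22% falling to 8%. The two planned comparisons would then be biased in opposite directions, by 0.25 to 0.35 SD (post-test) and 0.15 to 0.25 SD (change), and the planned baseline tests neither detect this reliably nor correct it. ANCOVA removes the conditional bias and lowers variance by about 15 to 25% against the change comparison, slightly less at these sizes. All of this rests on the assumed allocation method, sizes and r of 0.5 to 0.7.

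The lack of any description of sequence generation and concealment is a secondary, reporting point. It matters because, if the next assignment was known at enrolment, no adjustment could repair the resulting selection; the documents do not say whether it was.

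**What to change.** **Analysis.** Replace the between-arm t-test and the group-by-time test with an ANCOVA of each post-treatment outcome on group and that outcome's own baseline value, reporting the adjusted difference with its confidence interval. For pain the covariate is the pre-treatment NRS. Since NRS is recorded for several sites on three days of each cycle, the SAP should name the score used before and after treatment. Keep baseline values as a descriptive table and do not rely on significance tests of them.

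**Allocation.** State the ratio, how the sequence was made, who held it and how the next assignment was hidden until enrolment. If nothing hid it, say so and limit the claim accordingly. Blocking and stratification are optional; if they were used, describe them and put any stratification factor in the model.

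**Cost.** One SAP paragraph, one model term and one degree of freedom, with no new data. The Methods section reports treatment from November 2023 to January 2024 in the past tense, so a change to allocation may no longer be possible, whereas the analysis and the description can still be changed. If results by arm have already been seen, show the ANCOVA beside the planned tests and label it as added afterwards.
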